6.4.5. Follow-Up of Unresolved Adverse Events

Every reasonable effort will be made to follow subjects who have AEs.

Any AEs that are unresolved at the end of the subject's SFU visit are to be followed up by the Investigator until resolution or for as long as medically indicated. Additional information for any subject with an ongoing AE at the end of the SFU period may be requested by the [REDACTED] PHV, as needed.

6.4.6. Reporting Serious Adverse Events

Any AE that meets SAE criteria (Section 6.4.1.3) must be reported to the [REDACTED] PHV using the EDC system, immediately (i.e., within 24 hours) after the time site personnel first learn about the event.

In the event the EDC entry is not possible (e.g., system failure or access problems), the study site should complete the paper SAE report form and fax the form to the [REDACTED] PHV within 24 hours of awareness. The EDC system should be updated as soon as it is available.

A full description of every SAE will need to be provided to the [REDACTED] PHV (this may be supported by source documentation such as discharge summary or laboratory report should these documents be requested by the [REDACTED] PHV). Additional follow-up information, if required or available, should be sent to the [REDACTED] PHV as soon as possible and placed with the original SAE information.

The following contact information is to be used for SAE reporting:

[REDACTED] [REDACTED]
[REDACTED] [REDACTED]
[REDACTED] [REDACTED]

Information on non-serious AEs that become serious must also be reported to the [REDACTED] PHV as soon as it is available.

Investigators must report SAEs and follow-up information to their responsible Institutional Review Board (IRB) or Independent Ethics Committee (IEC) as applicable per institutional policy.

The Sponsor or designee will provide regulatory authorities, IRBs, IECs, and principal Investigators with clinical safety updates/reports according to local requirements.

6.4.6.1. Other Reasons for Immediate Reporting

The following events require reporting to the [REDACTED] PHV within 24 hours after the time the site personnel first learn about the event:

- Pregnancy in subject or female partner of male subject

- Overdose of the study drug or concomitant medication, regardless of whether it is considered AE
- Other study drug errors
- Any AE of malignancy (excluding basal cell carcinoma of the skin)

6.4.7. Pregnancy

Pregnancy is regarded as an AE only if there is a suspicion that study drug may have interfered with the effectiveness of a contraceptive medication. Nonetheless, any pregnancy that occurs during study participation (including pregnancy in a female partner of a male subject) must be reported to the [REDACTED] PHV in the same way and using the same procedures as for an SAE (Section 6.4.6). The subject with pregnancy must not receive (additional) study drug. The pregnancy must be followed up to determine outcome (including spontaneous miscarriage, elective termination, normal birth, or congenital abnormality) and status of mother and child, even if the subject was discontinued from the study. Pregnancy complications and elective terminations for medical reasons must be reported as an AE or SAE. Spontaneous miscarriage must be reported as an SAE.

Any SAE occurring in association with a pregnancy, brought to the Investigator's attention after the subject has completed the study, and considered by the Investigator as possibly related to the study drug, must be promptly reported to the [REDACTED] PHV.

In the event that a subject is found to be pregnant after having received at least 1 study drug dose, the study drug must be discontinued, and the pregnancy will be followed to term and the status of mother and child will be reported to the [REDACTED] PHV after delivery. Instances of perinatal death or congenital abnormality, if brought to the attention of the Investigator at any time after cessation of study drug, will be reported to the [REDACTED] PHV within 24 hours.

6.4.8. Evaluating and Reporting SUSARs

[REDACTED] Pharmacovigilance will promptly evaluate all SUSARs and nonserious AEs of special interest against cumulative product experience to identify and expeditiously communicate possible new safety findings to Investigators, IRBs/IECs, and applicable health authorities based on applicable legislation.

To determine reporting requirements for single SAE cases, [REDACTED] PHV staff in collaboration with Kiniksa Pharmaceuticals will assess the expectedness of these events using the Reference Safety Information (Section 6.2) of the rilonacept Investigator's Brochure.

[REDACTED] PHV will compare the severity of each SUSAR and the cumulative event frequency reported for the study with the severity and frequency reported in the applicable reference document.

Reporting requirements will also be based on the Investigator's assessment of causality and seriousness, with allowance for upgrading by [REDACTED] PHV and Kiniksa Pharmaceuticals as needed.

All relevant information about suspected SUSARs that are fatal or life-threatening will be recorded and reported to the competent authorities in all the applicable countries, and IRBs/IECs in conjunction with Directive 2001/20/EC.

6.5. Other Assessments

6.5.1. Pharmacokinetic Sample

All subjects will have PK samples obtained according to Section 13.1. For PK analyses, it is important that the exact time of the SC injection is recorded for each subject. When PK samples are to be collected on dosing days, serum will be collected pre-dose to measure rilonacept concentrations. Specific procedures for sample collection, processing, storage, and shipment can be found in a separate Laboratory Manual provided to sites.

A PK substudy will be conducted in a subset of subjects agreeing to provide a PK sample 24 hours after the first dose of study drug in the RI period. Specific procedures for sample collection, processing, storage, and shipment can be found in a separate Laboratory Manual provided to sites.

6.5.2. Anti-Drug Antibodies (ADAs) against Rilonacept (KPL-914)

Serum samples to measure the presence of ADAs against rilonacept will be collected according to Section 13.1. Instructions for sample collection, processing, storage, and shipment can be found in a separate Laboratory Manual provided to the site.

6.5.3. Biomarkers

Serum and plasma will be collected according to Section 13.1 for biomarker analysis.

6.5.4. Pharmacogenomics

Whole blood will be collected for pharmacogenomics assessments after signing the separate Pharmacogenomics ICF.

6.6. Laboratory Analyses

Any abnormal laboratory test results (hematology, chemistry, or urinalysis) or other safety assessments (e.g., physical examination, vital signs measurements), including those that worsen from baseline, felt to be clinically significant in the medical and scientific judgement of the Investigator are to be recorded as AEs or SAEs.

Laboratory assessments will be performed at study visits as summarized in Section 13.1. Unscheduled laboratory assessments for safety issues are permitted as deemed necessary by the Investigator.

Whenever possible in pediatric subjects, local laboratory tests should be drawn using pediatric tubes.

6.6.1. Serology

Samples for local or central laboratory assessment of hepatitis B surface antigen, hepatitis B core antibody, hepatitis C virus antibody, and HIV test will be collected at screening. If clinically indicated, those tests may be also collected during the study.

6.6.2. Hematology

Hematology tests performed at central study laboratory include WBC count with differential, platelet count, red blood cell count, mean corpuscular volume, hemoglobin, mean corpuscular hemoglobin concentration.

6.6.3. Chemistry

Blood chemistry tests performed in the central study laboratory include albumin, total protein, alkaline phosphatase, ALT/SGPT, AST/SGOT, direct bilirubin, total bilirubin, bicarbonate, chloride, potassium, sodium, creatinine, glucose.

In addition, the following chemistry tests may be performed together with local CRP measurement when using POC device: chloride, creatine kinase, creatinine, glucose, potassium, sodium, total carbon dioxide, blood urea nitrogen.

6.6.4. Non-fasting Lipid Panel

Subjects treated with riloncept may experience increases in their lipids, including total cholesterol, LDL, HDL, and triglycerides.

Non fasting measurements of total cholesterol, triglycerides, HDL, and direct LDL will be performed by central study laboratory as described in Section 13.1.

Investigators should monitor the lipid profiles in study subjects and consider ordering fasting lipid panel and/or lipid lowering therapies as needed based on cardiovascular risk factors and current guidelines.

6.6.5. Urinalysis

Urinalysis performed by the central study laboratory includes specific gravity, pH, protein, urobilinogen, ketones, glucose, blood, bilirubin, nitrites, leukocyte esterase. It will be performed as described in Section 13.1.

6.6.6. Pregnancy Test

For women of child-bearing potential, a urine pregnancy test using a licensed test (dipstick) should be performed prior to receiving the first administration of study drug and as needed during the study. When needed, serum pregnancy test should be performed. The purpose of pregnancy test is to prevent embryo/fetal exposure to study drug. Subjects with positive or indeterminate pregnancy test during the screening are not eligible for the study.

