For those subjects who, upon the 18-month post-most-recent-recurrence assessment, opt to continue in the LTE for observation only while off-treatment: should they have a further pericarditis recurrence, in the opinion of the Investigator, during that observation period, may resume open-label rilonacept after completion of a recurrence visit as outlined in Section 6.1.4. Resumption of rilonacept will follow the procedures for bailout as outlined in Section 3.1.3.

Subjects who experience a recurrence of pericarditis in the LTE while receiving open label riloncept will attend for a recurrence visit and may then continue on riloncept or transition to SOC treatment at the discretion of the investigator.

Figure 2: Overview of KPL-914-C002 Study Design

AEs, adverse events; CRP, C-reactive protein; CS, corticosteroid; NRS, Numerical Rating Scale; NSAIDs, nonsteroidal anti-inflammatory drugs; SC, subcutaneously.
*Duration of the run-in period undisclosed in order to maintain patient blinding to the start of the randomized-withdrawal period.
Index flare correspond to the last flare reported by subject in Rhapsody (i.e. Day 1/BL if no other flares reported, or otherwise latest post Baseline)

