The rationale for bailout rilonacept treatment upon pericarditis recurrence for subjects who were randomly assigned to placebo is that rilonacept had controlled their disease activity during the RI period; therefore, re-initiation of rilonacept is justified to regain control of pericarditis signs and symptoms upon recurrence. Subjects who were randomly assigned to rilonacept and qualify for bailout rilonacept upon pericarditis recurrence in the RW period were initial responders to rilonacept treatment during the RI period; thus it could be assumed that the loss of response during the RW period could be due to development of resistance to rilonacept due to different mechanisms, e.g., higher IL-1 levels or a change in rilonacept pharmacokinetics (PK)/ pharmacodynamics. Therefore, re-administration of a loading dose of rilonacept may help to restore Clinical Response.

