5.2.1. Adult Subjects (≥ 18 years old)

Rilonacept: Loading dose 320 mg administered as 2 SC injections, 160 mg each (2 ml) at RI baseline, followed by once-weekly SC injections of 160 mg (2ml).

Placebo: administered as once-weekly SC injections of 2 ml each in the RW period

Upon meeting protocol criteria for bailout rilonacept (Sections 3.1 and 6.2.3) in the RW period, subjects will be transitioned to open-label rilonacept 320 mg administered as 2 SC injections, 160 mg each (2 ml) at the next scheduled study drug administration date, followed by once-weekly SC injections of 160 mg (2ml).

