6.1.4. Pericarditis Recurrence Assessment: Clinic Visit

If a subject experiences symptoms consistent with pericarditis recurrence, he/she should contact the study Investigator immediately for evaluation (including in the LTE). It is possible that a subject may have assessments performed remotely, however, assessments are also expected to be performed at the study site as soon as possible. Required assessments include:

- Evaluate pericarditis pain on the 11-point NRS.
- Evaluate concomitant medications as well as pericarditis concomitant medications.
- Obtain laboratory samples for CRP (local and central) (the POC device provided by Kiniksa Pharmaceuticals is the preferred method for local laboratory CRP assessment).
- Acquire a 12 lead ECG.
- Acquire a cardiac ECHO per core laboratory imaging parameters; this ECHO is read locally for the purpose of pericarditis recurrence assessment and is then submitted to the ECHO core laboratory for central review.
- Perform an abbreviated physical examination, height and body weight.
- For subjects >18 years, complete the SF-36, EQ-5D-5L, ISI.
- For all subjects, complete the PGIPS score.
- The Investigator is to complete the PGA PA.
- Obtain central laboratory samples for PK, ADAs, and biomarkers.
- Other procedures deemed necessary per the Investigator or delegated site personnel (e.g. MRI for sub-study subjects).

Upon having completed the evaluation, if the Investigator makes a clinical diagnosis that the subject is having a pericarditis recurrence event, he/she should contact the [REDACTED] medical monitor to review and confirm that all assessments have been performed and collected. Upon [REDACTED] medical monitor confirmation of completion of the assessment, the Investigator commences as described in Section 6.2.3.

Subjects treated for a pericarditis recurrence event will continue to follow the same visit schedule described for the RW period (Section 6.1.5).

Source documentation including the assessments and evaluations used to confirm a pericarditis recurrence event, are required to be sent to CEC.

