6.2.3. Management of Suspected Pericarditis Recurrence in the RW Period

Pericarditis Recurrence Definition: Pericarditis recurrence, for the purpose of the protocol, is defined as the recurrence of typical pericarditis pain associated with supportive objective evidence of pericarditis.

At any time point during the RW period, subjects who experience suspected recurrence of their pericarditis will have been instructed to inform their site Investigator as soon as possible. Subjects who experience a suspected recurrence of pericarditis symptoms will be requested to report to the study site/clinic for a scheduled or unscheduled visit, during which clinical assessments will be performed to gather all the necessary diagnostic data to confirm or rule out the presence of pericarditis recurrence (Section 6.1.4). The Investigator will evaluate all assessments performed for a diagnostic workup, whether at the study site or at locations outside.

Upon completion of pericarditis workup, the Investigator is required to contact the [REDACTED] [REDACTED] medical monitor to confirm that the protocol required diagnostic workup is complete prior to implementing treatment for the event.

[figure not shown]
Following communication with the [REDACTED] medical monitor, if the event meets the criteria for bailout riloncept (at least 1 day with pericarditis pain measurement ≥ 4 on the 11-point NRS and one CRP value ≥ 1 mg/dL either on the same day or separated by no more than 7 days), and after the [REDACTED] medical monitor has confirmed with the Investigator that the diagnostic workup is complete, the attainment of bailout criteria is confirmed in the IWRS, blinded study drug is discontinued, and open-label riloncept treatment is dispensed. If needed, sequential ORT is allowed as outlined in Section 5.6.3. The subject will continue to be followed up according to Section 13.1 for the RW period.

Following communication with the [REDACTED] medical monitor, if the event does not meet the protocol criteria for bailout riloncept but in the judgement of Investigator requires treatment, after the [REDACTED] medical monitor has confirmed with the Investigator that the diagnostic workup is complete, the Investigator is allowed to add sequential ORT to blinded study drug, and as outlined in Section 5.6.3. Blinded study drug treatment will continue until a pericarditis recurrence that meets criteria for bailout riloncept, or until the end of the RW period.

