- l Adverse event reporting begins following the subject providing informed consent.
- m All procedures are to be completed prior to study drug administration.
- o Study drug administration is once weekly with a minimum of 5 days required between doses.
- s PK and ADA samples will be collected prior to study drug administration. PK at enrollment/baseline will be taken from ADA. As required, ADA samples will be collected at EOS, ET, and Unscheduled visits.
- z The MRI to occur only if the previous MRI was done longer than 6 months ago.
- aa Visit to occur 18 months from most recent documented recurrence.
- bb Samples collected every 24 weeks.

Table 5: Study Schedule of Activities – Supplemental Visits

Visit Name	PERICARDITIS RECURRENCE ASSESSMENT	END of TREATMENT (EOT) ^x	SAFETY FOLLOW UP (SFU) ^y (6 weeks post last dose)
Visit Window ^b (days)	N/A	N/A	+/- 2
Visit Type	Clinic	Clinic	Clinic or TC/RN
Concomitant medications	X	X	X
Pericarditis Concomitant medications	X	X	X
Full Physical Examination ^c		X	
Abbreviated Physical Examination ^d	X		
Body weight and height	X		
12-Lead ECG	X	X	
Echo ^e	X ^e	X	
MRI (substudy only)		X ^z	
Pericardial pain (11-point NRS)	X	X	
EQ-5D	X	X	
SF-36	X	X	

Visit Name	PERICARDITIS RECURRENCE ASSESSMENT	END of TREATMENT (EOT) ^x	SAFETY FOLLOW UP (SFU) ^y (6 weeks post last dose)
Visit Window ^b (days)	N/A	N/A	+/- 2
Visit Type	Clinic	Clinic	Clinic or TC/RN
ISI	X	X	
PGIPS	X	X	
PGA-PA	X	X	
Hematology, Chemistry Labs (Central)		X	
Lipid Panel (Central) ^h		X	
CRP (Local)	X		
CRP(Central	X	X	
PK (Central) ^s	X	X	X
ADA (Central) ^s	X	X	X
Biomarkers (Central)	X	X	
Urine Pregnancy ^j (Local or Central)			X
Urinalysis		X	
IWRS Subject Status Update	X ^s	X	
IWRS Weight Input (pediatric only)	X		
IWRS Drug Dispensing	X		
Study Drug Compliance Review	X	X	
Assessment of Pericarditis Recurrence	X	X	X
Adverse Event Reporting ^l	X	X	X

- b Scheduling of visits within visit windows requires cautious planning to ensure there is no interruption to subject evaluation and study drug treatment.
- h Lipid panels are non-fasting and are to be drawn at a minimum of every 6months during the randomization withdrawal and LTE periods, or more frequently as needed, with mandated evaluations as detailed in the schedule of events.

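### Version 3.0 requires a pregnancy test before the first dose, but none at the recurrence visit before rilonacept is re-started with a loading dose

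*Protocol*

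**What the plan says.** All references are to Protocol Version 3.0.

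- **The rule.** Section 6.6.6 says that the urine test "should be performed prior to receiving the first administration of study drug and as needed during the study", and that the purpose of the "pregnancy test is to prevent embryo/fetal exposure to study drug". Footnote j to the schedules makes it mandatory at enrollment and 6 weeks after the last dose. Repeats in between are allowed, not required.
- **Re-start after placebo.** For placebo subjects with a recurrence, Section 3.3 reasons that rilonacept had controlled their disease in the run-in: "therefore, re-initiation of rilonacept is justified to regain control of pericarditis signs and symptoms upon recurrence". Section 5.2.1 gives the adult dose: "subjects will be transitioned to open-label rilonacept 320 mg administered as 2 SC injections".
- **Re-start after observation.** Under Section 3.1.4, a subject who is off treatment in the long-term extension (LTE) and has a recurrence "may resume open-label rilonacept after completion of a recurrence visit as outlined in Section 6.1.4", following the bailout procedure.
- **The recurrence visit.** The required assessments in Section 6.1.4 include "Obtain central laboratory samples for PK, ADAs, and biomarkers" but no pregnancy test. In Section 6.2.3, once the workup is complete, "the attainment of bailout criteria is confirmed in the IWRS, blinded study drug is discontinued" and open-label drug is dispensed. No test is among those steps. In Table 5 the urine pregnancy row is marked at the safety follow-up only.
- **The withdrawal period.** Table 2 marks no test at RI Week 12/RW Baseline. Table 3 marks one only at the EORW visit, which is also LTE Baseline.

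**The concern.** The protocol tests before rilonacept is first given because the drug may cause fetal harm (Section 1.3.1). Section 6.4.7 forbids further dosing in pregnancy, and Section 4.3.2.1 stops study drug permanently. Those rules act only on a pregnancy that is known.

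A woman who conceives on placebo, or while under observation, is not being given rilonacept at that time. The recurrence visit is the last point at which a test can keep her from being dosed while pregnant, and the dose that follows is a loading dose. Under Section 3.1.3 bailout is prescribed once the pain and CRP criteria are met, so a site can follow every written step and still dose an unrecognized pregnancy. The stake is patient safety. No efficacy estimate, error rate or power figure is affected.

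**Working it through.** **1. Places where rilonacept is started or re-started**

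| Start | Test required or scheduled beforehand? | Source |
|---|---|---|
| First dose, RI Baseline | Yes | Section 6.6.6; Table 2 |
| LTE Baseline, placebo woman without recurrence | Yes, marked at EORW on the same day | Table 3; Section 6.1 places assessments before the injection |
| Bailout in RW, placebo woman with recurrence | No | Sections 6.1.4 and 6.2.3; Table 5 |
| Resumption from the LTE observation arm | No | Section 3.1.4, which relies on Section 6.1.4 |

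A placebo woman who does not recur is therefore scheduled for a test before rilonacept resumes, and one who does recur is not. The Table 5 reading depends on column position in text extracted from a PDF, but the Section 6.1.4 list and footnote j agree with it.

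**2. Number of placebo recurrences.** Inputs from Section 7.4: 25 per arm, placebo median 8 weeks, hazard ratio 0.244, exponential times, 22 events.

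- Placebo hazard = ln 2 / 8 = 0.0866 per week. Rilonacept hazard = 0.244 × 0.0866 = 0.0211 per week.
- With equal follow-up t, solve 25(1 − e^(−0.0866t)) + 25(1 − e^(−0.0211t)) = 22. This gives t = 12.2 weeks, with 16.3 placebo and 5.7 rilonacept events.
- If randomization is spread evenly over 52 weeks (an assumption) and the cut is at the 22nd event, simulation gives a mean of 15.1 placebo events.

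So about 15 to 16 placebo recurrences. Only those that meet the bailout criteria are re-starts.

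**3. Women of childbearing potential.** The share is not given. At an assumed 20% to 50%: 16 × 0.2 = 3.2 and 16 × 0.5 = 8. These are re-starts without a required test, not pregnancies.

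**4. Time since the last scheduled test.** At the placebo median this is 12 run-in weeks + 8 weeks = 20 weeks. The 12 run-in weeks were on active drug, so a conception then has already been exposed. Only the 8 placebo weeks are time in which a woman could conceive while not being dosed.

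**5. Expected pregnancies.** Take 8 weeks as the typical time on placebo and assume contraceptive failure of 1% to 5% per year (not given in the document).

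- Low: 3 × 8/52 = 0.46 woman-years; × 0.01 = 0.005.
- High: 8 × 8/52 = 1.23 woman-years; × 0.05 = 0.06.
- High, counting all 20 weeks: 8 × 20/52 × 0.05 = 0.15.

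**6. LTE observation arm.** Its size is not given, so no count is possible. These women have a test at the 18-month review (Table 4) and a required one at the safety follow-up (footnotes j and y). None is then required before resumption.

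**The case against.** The strongest case against is that this is one consistent scheme and not an error. Study drug is defined in Section 5.2 as rilonacept and placebo together, so its first administration happens once, at RI Baseline. No rule says that every start of rilonacept needs a test. A reader might infer that the protocol breaks its own rule; the text does not support that. What stands against the plan is narrower: the stated purpose of the test applies equally to a second start, and Version 3.0 schedules a test at one re-start point and not at the other.

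There are real safeguards. Contraception is mandatory throughout (Section 4.1, criterion 8d), planning a pregnancy is an exclusion, subjects are contacted every 4 weeks in the withdrawal period and asked about changes in well-being, and the investigator may test or add procedures at any time. These make the risk small. They do not make the test happen, and contraception was already an entry condition when a test before the first dose was still thought necessary.

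A test at re-start would also not rule out all exposure. Contraception is required for 3 months after the last dose, which suggests that the drug is treated as relevant for some time after dosing stops. That stands: the test prevents new dosing in pregnancy, not every exposure.

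A reader might also infer that routine tests are needed at RI Week 12 and at each withdrawal and LTE clinic visit. The document sets no maximum interval, and for a woman already on drug such tests only limit the duration of exposure. That is a preference and is not recommended here.

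**Conclusion.** The point holds as a cheap improvement for patient safety. As written, a woman who has been on placebo, or off treatment under observation, can receive a rilonacept loading dose with no required pregnancy test at that visit, while the same protocol tests before the first dose and schedules a test before LTE dosing.

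The size is modest. It comes to perhaps 3 to 8 untested re-starts in the placebo arm, resting on the Section 7.4 assumptions and an assumed 20% to 50% share of women of childbearing potential, and fewer if some recurrences do not meet the bailout criteria. Expected pregnancies are well below one: about 0.005 to 0.06 over the placebo time, under an assumed failure rate of 1% to 5% per year. It would be wrong to read 3 to 8 as pregnancies, or the 20-week gap as 20 weeks off drug. The case for change rests on a serious possible harm set against a negligible cost, not on frequency.

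**What to change.** For women of childbearing potential, in both randomized arms so that the blind is kept:

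1. Add a urine pregnancy test to the required list in Section 6.1.4 and to the recurrence column of Table 5.
2. In Section 6.2.3, require a negative result before the bailout loading dose. In Section 3.1.4, state that the same applies to resumption from the LTE observation arm.
3. If the result is positive or indeterminate, hold rilonacept and do the serum test that Section 6.6.6 already provides for.

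For a woman randomized to rilonacept, who has been dosed weekly, the test only limits further exposure. She is included to protect the blind.

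The running cost is one dipstick at a clinic visit that already includes blood samples, ECG and echocardiography, with no extra visit. An occasional false positive may briefly delay the open-label dose. Section 5.6.3 already imposes a wait of at least 5 days from the last blinded dose and allows sequential oral rescue therapy meanwhile. The change needs an amendment with ethics approval (Section 11.2.1) and could be bundled with the next one.
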